### **3.2 Study Primary and secondary outcome measures**

The second phase of the study is a qualitative study that includes interviews and focus groups. Factors that influence the decision-making process during choice of PC treatment, and information needs of these groups of people will be explored. For the test/evaluation phase of the study, the primary outcome measures are the decisional conflict and system usability score. These will be measured with the DCS and (adaptions of) the System Usability Scale (SUS) (Brooke 1996), respectively.

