## Study synopsis

Study title	Shared decision-making: investigating the potential of an interactive, web-based information tool to support treatment choice of people with advanced pancreatic cancer
Sponsor Reference No.	
Study design	Multiphase mixed methods design
Study participants	Oncologists, clinical nurse specialists, people diagnosed with advanced pancreatic cancer, and their relatives who provide care and support for them
Sample size	120
Follow-up duration	Not applicable
Planned study period	August 2018 – December 2019
Primary objectives	To investigate the potential of a web-based, interactive, information tool in facilitating shared decision-making for the choice of treatment for people with advanced pancreatic cancer (APC)
Secondary objectives	
 
(i) To assess the quality of life, efficacy, and safety of chemotherapy treatments of APC through systematic review and network meta-analysis (NMA) of randomized controlled trials (RCTs).
 
(ii) To explore the expectations and preferences of clinicians, people with APC, and their relatives, when making decisions about treatment, through focus groups and semi-structured interviews for clinicians, and people with APC (including their relatives), respectively.
 
(iii) To identify the features necessary for the design of a web-based information tool to facilitate SDM between clinicians and people with APC about choice of treatment.
 
(iv) To evaluate the effectiveness of the developed information tool in SDM, through a pilot test with clinicians (doctors and nurse specialists), people with APC, and their relatives.
 

Primary endpoint	Effectiveness of Shared decision-making
Interventions	Not applicable

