### **2.2 Second objectives**

- (i) To assess the quality of life, efficacy, and safety of chemotherapy treatments of APC through systematic review and network meta-analysis (NMA) of randomized controlled trials (RCTs).
- (ii) To explore the expectations and preferences of clinicians, people with APC, and their relatives, when making decisions about treatment, through focus groups and semi-structured interviews for clinicians, and people with APC (including their relatives), respectively.
- (iii) To identify the features necessary for the design of a web-based information tool to facilitate SDM between clinicians and people with APC about choice of treatment.
- (iv) To evaluate the effectiveness of the developed information tool in SDM, through a pilot test with clinicians (doctors and nurse specialists), people with APC, and their relatives.

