### **3.1.5 Phase 4: Evaluation of developed information tool**

The resulting web-based information tool will be tested for its functionality, usability, and effectiveness in SDM. Target users are clinicians, patients and relatives of patients. Users will be asked to perform certain tasks with the developed tool. These tasks will be based on the expected functionalities of the proposed information tool. Phase 2 will elicit some of the requirements and functionalities of the proposed information tool.

Phase 4 is designed to be accomplished in two stages:

Stage 1 will assess the information tool's usability. It will be for participants who were involved in the study during the focus group or semi-structured interviews (phase 2). Participants will be asked to complete predefined tasks using the information tool. Participants will then provide feedback to inform the tool modification. There will be options to accomplish the tasks from the residence of participants through web links to the information tool and an online feedback form. Feedback is in the form of a questionnaire and open-ended questions.

Data from stage 1 is primarily for refining the information tool's functionality and usability in preparation for stage 2.

The average duration for stage 1 test is 30 minutes.

Stage 2 will evaluate the effectiveness of the proposed information tool in the SDM process. It is targeted at real-life consultations between clinicians and patients who are starting consultations about their treatment. These patients and relatives will be recruited for this stage. Evaluation at this stage involves the effectiveness of the decision-making process and decision quality (Sepucha et al. 2013) of the information tool.

Effectiveness of the decision-making process is the extent to which the information tool helps the participants in the SDM process. However, decision quality or quality of choice measures the extent to which patients are fully informed and receive the treatments consistent with their preferences (Sepucha et al. 2013).

A variety of instruments have been proposed for measuring the effectiveness of SDM process (Scholl et al. 2011) and the effectiveness of decision aids (Sepucha et al. 2013). The Decision Conflict Scale (DCS) (O'Connor 1995) will be adopted for this purpose because it has been validated in many studies, it has more than one version to suit different participants (Légaré et al. 2012), and it is freely available.

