After each consultation involving SDM with the information tool, all participating parties (clinician, patient, relative) will fill out the appropriate DCS form. The form is to be completed and returned within 4 weeks after consultation. This is to enable the participants to give a reliable evaluation of their experience during the consultation.

The instruments can be returned at the hospital, by email, or post (stamped addressed envelopes will be provided).

Electronic versions of the DCS will be developed and interested participants can choose to provide feedback through this option.

The duration for filling the DCS form is approximately 10 minutes.

To assess the decision quality associated with the information tool, Sepucha et al. (2013) noted that more than half of the tools reported in the literature were original products designed to meet the requirements of each study. Consequently, the development of a customised instrument to assess the quality of the decision associated with the proposed information tool may be explored. As in the case of breast cancer decision quality measurement (Sepucha et al. 2007; Lee et al. 2010), the major contents of the decision quality instrument for APC treatment will be

disease-specific knowledge and value items or goals of the treatment for people with APC.

The content of the proposed instrument will require about 10 minutes to complete.

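### Does naming the System Usability Scale score as a primary outcome, with no stage or tool version, leave the primary endpoint unclear?

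*Protocol*

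**What the plan says.** Section 3.2 states that for the test/evaluation phase (Phase 4) "the primary outcome measures are the decisional conflict and system usability score", measured by the DCS and by the SUS or adaptations of it. It gives no stage and no tool version. Its heading covers primary and secondary measures, but nothing in it is labelled secondary.

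The synopsis gives a single primary endpoint: "Effectiveness of Shared decision-making". The primary objective (2.1) concerns the tool's potential to support shared decision-making (SDM). The objective that matches Phase 4, item (iv) in 2.2, is "To evaluate the effectiveness of the developed information tool in SDM".

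Section 3.1.5 opens Phase 4 by saying that the tool "will be tested for its functionality, usability, and effectiveness in SDM", and then splits the work into two stages:

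- **Stage 1** assesses usability. "Participants will then provide feedback to inform the tool modification", and "Data from stage 1 is primarily for refining" the tool ahead of Stage 2.
- **Stage 2** takes place in real consultations and covers the decision-making process and decision quality. The DCS is completed after each consultation and returned within 4 weeks.

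Section 3.3 ends the first stage with the return of usability forms and the second with the return of SDM forms. Section 8.1 plans descriptive statistics for the Phase 4 questionnaires and refers to the DCS manual. Section 5.2 says the study has one arm.

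**The concern.** A reader of 3.2 would report two primary outcomes, and a reader of the synopsis one. The two are not the same construct: 3.1.5 adopts the DCS to measure the effectiveness of the SDM process, and nothing in the protocol says that the SUS measures it.

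There is also a question of which tool is being described. If the SUS is taken only in Stage 1, it scores the tool before the Stage 1 feedback is acted on, while the DCS concerns the tool after that. A primary SUS score reported as 3.2 words it, with no stage or version, could be read as the usability of the tool that patients and clinicians used in consultations. The visible text plans no SUS score for that version. At stake would be which result is presented as the main one, and what the usability result is taken to describe.

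**Working it through.** The protocol states no figure for this point, so the check is mainly a comparison of sections.

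**1. Is the mismatch of labels real?** Yes. Section 3.2 names two primary measures and the synopsis one endpoint. They are set at different levels: the synopsis names a construct for the whole study, and 3.2 names instruments for one phase. That softens the mismatch but does not remove it. None of the five objectives (1 primary + 4 secondary) names usability. This is only a count of words, however. The primary objective is broad, and secondary objective (iii) concerns the features the tool's design needs.

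**2. Can the stage and version be recovered from the protocol?**

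| Question | SUS | DCS |
|---|---|---|
| Stage | Stage 1 (3.1.5) | Stage 2, after each consultation (3.1.5) |
| Form that ends the stage (3.3) | Usability form | SDM form |
| Tool version | Before refinement, since Stage 1 data are used to refine it | After refinement |
| Planned number of tests (8.2) | At least 5 + 5 + 5 = 15 | 30 |

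Both can be recovered. An analyst who follows 3.1.5 and 3.3 arrives at one reading: the SUS describes the Stage 1 tool and informs its revision, and the DCS describes the tool used in consultations.

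**3. Does anything depend on the label?** Section 8.1 plans descriptive statistics, section 5.2 describes a single arm, and the protocol sets no hypothesis test or success threshold for either measure. The Stage 2 number in 8.2 comes from a published recommendation of 20 to 25 for a single group, raised to 30 for incomplete questionnaires. It does not rest on one or two primary outcomes. The Stage 1 minimum is a count by participant group. There is no error rate to share between outcomes.

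**4. Would a SUS form at Stage 2 help?** It would give a score for the refined tool, at a cost in time. On the DCS the protocol says "The duration for filling the DCS form is approximately 10 minutes". On the decision-quality instrument, whose development is described only as a possibility, it says "The content of the proposed instrument will require about 10 minutes to complete". Section 7.3 and Table 2 both give 20 minutes. The protocol gives no time for the SUS; 2 to 5 minutes is assumed here.

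- DCS + SUS: 10 + 2 = 12 to 10 + 5 = 15 minutes, within 20.
- DCS + decision-quality instrument: 10 + 10 = 20 minutes, with nothing left over.
- All three: 20 + 2 = 22 to 20 + 5 = 25 minutes, which is 2 to 5 minutes over.

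**The case for a change.** The strongest case for a change is that stating what is primary belongs in the protocol and is not a detail left to an analysis plan. This protocol states it twice and differently. Inferring the stage does not settle whether there are one or two primary outcomes. Even in a descriptive study, the label decides which result leads the report. Calling a measure primary when its data serve mainly to alter the thing being measured also deserves an explicit word, and 3.2 has none.

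The part about labels stands: 3.2 and the synopsis do not agree. The part about version is weaker, because the Stage 1 description in 3.1.5 already gives the formative purpose. A misreading requires taking 3.2 apart from the sections on either side of it. Section 8.1 does not mention the SUS by name, but it does take in the Phase 4 questionnaires generally, and scoring detail may properly sit in an analysis plan. The web analytics in 3.4 are not limited to Stage 1, but they yield no SUS score and so do not bear on the question.

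**Conclusion.** No change to the plan follows. The one real defect is clerical: two primary measures in 3.2 against one primary endpoint in the synopsis. Making the labels agree would be a one-line edit that alters no data, analysis, sample size or conclusion. The stage and tool version are clear once 3.1.5 and 3.3 are read together, and following the plan as written gives sound descriptive results for both scales. Testing usability before refining a tool is the usual order of development.

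A second SUS at Stage 2 would be a debatable trade-off. It would measure something no stated objective asks for, and would add burden for seriously ill patients and their relatives. It might also break the 20-minute limit, and answers could come up to 4 weeks after the tool was used.

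This conclusion rests on Phase 4 remaining descriptive and on the visible text. Figures 1 to 3 are not shown. If the recruitment figures placed a usability form at Stage 2, the worry about tool version would shrink further, while the mismatch of labels would remain.

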### **3.3 Definition of end of study**

There are two recruitment stages for this research study. For the first stage, end of study is when the participants have completed and returned the usability evaluation forms for the web-based information tool.

For the second stage, end of study is when participants have successfully completed and returned the SDM evaluation forms.

### **3.4 Data collection**

Data will be extracted from relevant literature for phase 1 of this research with the use of excel sheets specially designed for this purpose. This will enable synthesis of information regarding the comparative benefits, harms and uncertainties surrounding treatment options for APC.

Data collection for participants will be through recordings during interviews, and focus groups, and through completion of survey (paper-based or online). The interview and focus groups recordings will be used to identify themes that will broaden the knowledge on information needs, expectations and challenges of treatment choices for people with APC.

Web analytic tools like Google Analytics  will be included in the information tool to collect data on User Behaviour Flow.

The researcher will be responsible for data collection, transcription and analysis.

### **3.5 Source data**

Data sources are from the relevant literature (phase 1), and from participants responses during interviews, focus groups (phase2), and completed forms from phase 3 and phase 4. For monitoring and audit purposes, the recordings will kept for the duration of the permitted duration allowed by data protection act to facilitate comparison with corresponding transcriptions of interviews and focus groups.

## **4 Participant selection**

Participants shall be clinicians, patients with APC, and their relatives. They are defined in section 4.1.

### **4.1 Definition of participant groups**

*Clinician*: a trained medical professional who has had experience in discussing outcomes or treatment choices with patients about PC. A clinician can either be an oncologist or a clinical nurse specialist.

*Patient*: an adult who has been diagnosed with APC and who has discussed treatment choices or prognostic outcomes with a clinician.

 [https://www.google.com/analytics/analytics/#?modal\\_active=none](https://www.google.com/analytics/analytics/#?modal_active=none)

*Relative*: an adult who is involved in providing support for the patient during the period of treatment. They will normally be nominated by the patient.

## 4.2 Recruitment

Potential clinicians and patients will be recruited from NHS Trust sites in England, and through a charity, Pancreatic Cancer UK (PCUK). PCUK have been approached regarding their support for the research.

### 4.2.1 NHS recruitment

A member of the site's clinical care team will identify potential participants for the study either through medical records or during hospital appointments, and seek their permission to be contacted by the recruiter (researcher or onsite research nurse) regarding the research. This initial identification will include collection of the Participant Information Sheet (PIS) by the potential participants. There will be a minimum of 24 hours to expect a reply to the invitation.

The recruiter will contact interested persons (either during subsequent appointments, or by phone, or email, or through other agreed communication channels) and explain the study in more detail. If there are questions, these will be answered by the recruiter.

The potential participant will then be invited to sign the informed consent form to indicate acceptance of inclusion in the study.

For focus groups or face-to-face semi-structured interviews, the informed consent form can be signed the same day as the interview (prior to data collection). For interviews by phone or Skype (or other teleconferencing software), informed consent forms will be signed and returned by post, or email.

Relatives of patients will be invited through the patients who have agreed to join the study. The patients will be asked to give a copy of the PIS to their nominated relative with an invitation to take part in the study. The recruiter will then contact the relatives who have shown interest in the study. The most appropriate means and period of contact will be agreed by the recruiter and the patient who made the nomination.

The recruiter will receive informed consent from the relatives if they accept to take part in the study.

The recruitment of clinicians will be either by presentations during periodic meetings, or through other suitable channels at the Trust sites.

### 4.2.2 PCUK recruitment

For recruitment through PCUK, the project (including the PIS) will be advertised through PCUK online notice boards, and interested persons will be invited to contact the researcher through the BU Clinical Research Unit Patient and Public Involvement (BUCRU PPI). If the potential participants meet the inclusion criteria, written informed consent will be obtained (via post or email or through face to face contact, whichever is convenient).

### 4.2.3 Recruitment style

Recruitment will be by stratified sampling which is a subset of purposive sampling (Robinson 2014). Stratified sampling is a technique based on defining categories or groups of interest, splitting the sample according to these categories, and including suitable participants into these categories (Robinson 2014). The theoretical foundation for these categories (clinicians, patients, relatives) is explained in the shared model of decision making (Charles et al. 1999).

#### 4.2.4 Stages of recruitment

Figure 2 and Figure 3 describe the envisaged flow of activity for the two main stages of recruitment of participants described in section 3.3.

[figure not shown]

Figure 2: First Stage Recruitment

[figure not shown]

Figure 3: Second Stage Recruitment

#### 4.3 Pre-registration or randomisation evaluations

There are no additional screening procedures involved after potential participants have been identified by a member of the clinical team. There are no randomisation evaluation for this research study.

#### 4.4 Inclusion Criteria and exclusion criteria

Table 1 outlines the inclusion and exclusion criteria for participants of this research.

Table 1: Participant inclusion and exclusion criteria

	Participant	Inclusion criteria	Exclusion criteria
1.	Clinician (doctors, clinical nurse specialists)	Clinicians must have had experience of a minimum of one consultation with a patient with cancer leading to the administration of chemotherapy	Clinicians who have no prior experience in consultation with candidates for chemotherapy
2.	Patient	Diagnosed with advanced PC, able to speak and understand written English, 18 years or older	Patients with operable PC, Non-English speakers, Patients too weak to speak or give written informed consent, Patients lacking mental capacity to consent

Participant	Inclusion criteria	Exclusion criteria
3. Relative (or carer)	
must be involved in, or aware of, the decision of the patients in choice of treatment, should be responsible for the provision of support to the patient, Must 18 years or older, Must be able to speak and understand written English
	
Relative who is not involved in the decision-making process leading to treatment selection for the patient, Relative lacking mental capacity to consent

#### **4.5 Withdrawal criteria**

If a participant loses the capacity to consent through severe ill health or other reasons, they will be withdrawn from the study. This will be verified by the referring oncologist, or other persons acting on behalf of the participants. Before the commencement of each phase of the study, the capacity of participants to consent will be assessed by verbally reminding them of the purpose of the research and their responsibility, including their ability to leave the study at any time.

If a participant indicates interest to voluntarily withdraw, they will be withdrawn from the study.

### **5 Treatment or therapy plan**

#### **5.1 Description of Treatment or Therapy**

The intervention is a web-based interactive information tool that will be designed to provide the relevant information required to guide users in shared-decision-making about treatment options available for APC.

The intervention is not invasive and it will not affect care of participants.

#### **5.2 Treatment Arms**

This is a single arm study.

### **6 Assessment and follow-up**

#### **6.1 Duration of Treatment or Therapy**

There are no treatments involved this study.

#### **6.2 Duration of Follow-up**

Not applicable for this study.

#### **6.3 Subject compliance or Criteria for Removal from Study**

Compliance will be identified by completed and returned forms (whether by post or online). Follow-ups will mainly consist of phone calls and/or email reminders which will be agreed with participants for non-compliance.

### **7 Assessment of safety**

#### **7.1 Definition**

It is expected that this will be of minimal risk to the participants. However, the following issues have been considered.

## 7.2 Risks

Emotional distress is identified as a potential risk when patients and relatives are asked to discuss their experiences with respect to APC treatment. To manage this, the participants will be made aware of the nature of questions to expect before the start of the interviews through a pre-interview briefing with the researcher. They will be informed that they are free to pause or suspend their participation if and when they feel uncomfortable. Furthermore, contacts of professional counselling support at the hospital will be made available to the participants.

## 7.3 Burdens

The burdens for the participants shall be in the form of time spent in the focus groups and semi-structured interviews, completing questionnaires, and information tool testing. Efforts shall be made to ensure that a maximum of 1 hour is spent in the focus groups and the interviews. The filling of questionnaires and information tool testing will not exceed 20 minutes and 30 minutes, respectively. Different participants (patients and relatives) will be recruited for the Stage 2 of the Test phase (Phase 4). The venue of the focus groups shall be the hospitals. Interviews shall be conducted at the hospital in the first instance, or by phone, via Skype (or other teleconferencing application), or at the residence of participants (patients or relatives), if the other options do not meet the desired number of participants.

